11.1.3. Weight and Height

Height and weight will be captured as per the Schedule of Events. BMI will be calculated using the NIH website BMI calculator.

https://www.nhlbi.nih.gov/health/educational/lose_wt/BMI/bmicalc.htm

11.1.4. Electrocardiogram (ECG)

All scheduled ECGs will be performed after the patient has rested supine for approximately 5 minutes as per the schedule of events.

11.1.5. Physical Examination

A physical examination will be conducted and abnormalities will be described. After the initial full physical exam only symptom-driven examinations will be performed.

11.1.6. Laboratory Assessments

All laboratory assessments will be collected as per the schedule of events and as described in the study laboratory manual.

11.1.6.1. Hematology and Blood Chemistry

Clinical Laboratories (Hematology and Serum Chemistry) will be performed as per the schedule of events and will be described in the study laboratory manual.

11.1.6.2. Urinalysis

Urinalysis will be performed as per the schedule of events and will be described in the study laboratory manual.

Instruct patient to obtain a "clean-catch" urine sample, collected in midstream.

Protocol AVE-901-104 Phase 3 Open-Label Safety Study
Avenue Therapeutics, Inc.

Tramadol Infusion
August 29, 2018

11.1.6.3. Pregnancy Screen

Pregnancy screening will be performed for all females of childbearing potential in accordance with the schedule of events.

11.2. Adverse and Serious Adverse Events

11.2.1. Definition of Adverse Events

11.2.1.1. Adverse Event (AE)

Adverse event means any untoward medical occurrence associated with the use of a drug in humans, whether or not considered drug related. Adverse events may include safety findings considered to be clinically significant by the Investigator. An adverse drug event can therefore be any unfavorable and unintended sign (including an abnormal laboratory finding), symptom, or disease temporally associated with the use of a medicinal product, whether or not it is related to the medicinal product. Reporting an adverse event does not necessarily reflect a conclusion by the Investigator that the event is causally related to the drug.

All adverse events should be captured and documented along with any supporting documentation. Adverse events should be spontaneously reported or elicited by non-suggestive probing. Signs or symptoms associated with a worsening in either severity or frequency as compared to a baseline condition should be evaluated by the Investigator for clinical significance and adverse event reporting.

Each adverse event in this study will be assessed for Grade, where Grade of an AE refers to the severity of the AE. Grade will be assessed according to CTCAE Version 4.03 or higher. The CTCAE displays Grades 1 through 5 with unique clinical descriptions of severity for each AE that are based on this general guideline. [Table 6](#) provides the CTCAE grades and grade descriptions to be used in this study.

Table 6: CTCAE Grade (Study AVE 901-104)

CTCAE Grade	CTCAE Grade Description
Grade 1: Mild	Asymptomatic or mild symptoms; clinical or diagnostic observations only; intervention not indicated.
Grade 2: Moderate	Minimal, local or noninvasive intervention indicated; limiting age-appropriate instrumental ADL ¹ .
Grade 3: Severe	Severe or medically significant but not immediately life-threatening; hospitalization or prolongation of hospitalization indicated; disabling; limiting self-care ADL ² .
Grade 4: Life-threatening	Life-threatening consequences; urgent intervention indicated.
Grade 5: Death	Death related to the AE.

Activities of Daily Living (ADL)

¹ Instrumental ADL refer to preparing meals, shopping for groceries or clothes, using the telephone, managing money, etc.

² Self-care ADL refer to bathing, dressing and undressing, feeding self, using the toilet, taking medications, and not bedridden.

National Cancer Institute Common Terminology Criteria for Adverse Events (NCI-CTCAE), Version 4.03 will be used for AE grading. A complete CTCAE list can be downloaded at <http://evs.nci.nih.gov/ftp1/CTCAE/About.html>.

11.2.1.2. Serious Adverse Event (SAE)

A serious adverse event is an AE occurring during the study that fulfills one or more of the following:

- Results in death
- It is immediately life-threatening
- It requires in-patient hospitalization or prolongation of existing hospitalization
- It results in persistent or significant disability or incapacity
- Results in a congenital abnormality or birth defect
- It is an important medical event that may jeopardize the patient or may require medical intervention to prevent one of the outcomes listed above

Reporting serious adverse events requires additional detailed reports and follow-up, depending upon the Investigator's estimate of a causal relationship between the test agent and the adverse event(s), and whether the adverse event(s) is identified in nature, severity, and frequency in the Investigator's Brochure or other risk information supplied to the Investigator.

All serious adverse events (SAEs) should be submitted promptly to the Institutional Review Board/Independent Ethics Committee (IRB/IEC). The investigator must make an effort to obtain all hospital medical records including discharge summary confirming final diagnosis. The death of a patient must be immediately (within 24 hours) reported to the IRB. All serious and non-

serious adverse events should be thoroughly documented and followed out by the Investigator until the event resolves or until the termination visit. The event may be followed longer, if deemed necessary. For any death occurring during the trial, the medical condition that led to the death should also be noted. The “outcome” status should be noted as “death” in these cases of SAEs that resulted in death. In addition, all SAEs that occur from treatment through the follow-up phone call should be recorded and reported as noted previously.

11.3. Relationship to Study Drug

An Investigator who is qualified in medicine must make the determination of relationship to the investigational product for each AE. The Investigator should decide whether, in his or her medical judgment, there is a reasonable possibility that the event may have been caused by the investigational product. For purposes of the definitions below, “temporal sequence” is defined as an association between administration of a drug and the observed reaction or event such that the drug was present prior to the reaction or event.

DEFINITE - The adverse event:

- follows a reasonable temporal sequence from drug administration,
- abates upon discontinuation of the drug (dechallenge), AND
- is confirmed by reappearance of the reaction on repeat exposure (rechallenge).

PROBABLE - The adverse event:

- follows a reasonable temporal sequence from drug administration,
- abates upon discontinuation of the drug (dechallenge), and
- cannot be reasonably explained by the known characteristics of the patient’s clinical state.

POSSIBLE - The adverse event:

- follows a reasonable temporal sequence from drug administration, and;
- could have been produced by the patient's clinical state or by other modes of therapy administered to the patient.

REMOTE

- There is another more likely explanation for the adverse event, such as a concomitant therapy or procedure. The known pharmacology of the drug is not consistent with the event and the temporal relationship to study drug is unknown or may be consistent with the drug being present at the time of event.

DEFINITELY NOT – The adverse event:

- is definitely produced by the patient's clinical state or by other modes of therapy administered to the patient. The temporal relationship indicates that the drug was not present at the time of the event.

11.4. Recording Adverse Events

Adverse events spontaneously reported by the patient/caregiver and/or in response to an open question from the study personnel or revealed by observation will be recorded during the study at the investigational site. The AE term should be reported in standard medical terminology when possible. For each AE, the Investigator will evaluate and report the onset (date and time), resolution (date and time), severity, causality, action taken, serious, outcome (if applicable), and whether or not it caused the patient to discontinue the study.

It is important to distinguish between serious and severe AEs. Severity is a measure of intensity whereas seriousness is defined by the criteria under Section 11.2.1.2. An AE of severe intensity may not be considered serious.

Should a pregnancy occur, it must be reported and recorded on a pregnancy reporting form. Pregnancy in itself is not regarded as an AE unless there is a suspicion that an investigational product may have interfered with the effectiveness of a contraceptive medication.

The outcome of all pregnancies (spontaneous miscarriage, elective termination, normal birth or congenital abnormality) must be followed up and documented even if the patient was discontinued from the study.

All reports of congenital abnormalities/birth defects are SAEs. Spontaneous miscarriages should also be reported and handled as SAEs. Elective abortions without complications should not be handled as AEs.

11.5. Reporting Adverse Events

Information about AEs and SAEs will be collected from treatment (i.e. from time of first dose) through the follow-up phone call. AEs or SAEs occurring prior to first dose of study treatment will be considered Medical History. AEs or SAEs occurring during or after the first dose of study treatment will be treatment-emergent (S)AE. Any SAEs considered at least possibly related to the investigational product and discovered by the Investigator at any time after the study should be reported. The Investigator must complete, sign and date the SAE pages, verify the accuracy of the information recorded on the SAE pages with the corresponding source documents.

Additional follow-up information, if required or available, should all be communicated within one business day of receipt and this should be completed on a follow-up SAE form and placed with the original SAE information and kept with the appropriate section of the eCRF and/or study file.

The Sponsor is responsible for notifying the relevant regulatory authorities of certain events. It is the Investigator's responsibility to notify the IRB of all SAEs that occur at his or her site. Investigators will also be notified of all unexpected, serious, drug-related events (7/15 Day Safety Reports) that occur during the clinical trial. Each site is responsible for notifying its IRB or IEC of these additional SAEs.

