7.2. Patient Exclusion Criteria

The following are patient exclusion criteria for this study; each patient must **not** meet any of these exclusion criteria in order to be enrolled into this study.

1. The patient has current or historical evidence of any clinically significant disease or condition that might place the patient at unacceptable risk due to receiving the study medication, in the opinion of the investigator.
2. The patient has allergy or hypersensitivity (or is intolerant) to opioids or tramadol.

3. The patient has used chronic opioid therapy, defined as ≥ 20 MEQs of morphine per day ≥ 3 days out of 7 days over the past 4 weeks.
4. The patient has a recent (within 2 years) and/or current history of alcohol, opiate or tranquilizer abuse or dependence.
5. The patient is taking herbal or dietary supplements or medications that are moderate or strong inhibitors of CYP2D6 or CYP3A4 (e.g., fluoxetine, paroxetine, amitriptyline, quinidine, ketoconazole, erythromycin, grapefruit juice) or inducers of CYP3A4 (e.g., carbamazepine, rifampin, St. John's Wort) and cannot go through a minimum washout period of 7 days prior to surgery.
6. The patient has a history of epilepsy, is susceptible to seizures.
7. The patient cannot be withdrawn from medications (at least 7 days prior to surgery) that may lower the seizure threshold (e.g. anti-psychotic agents, MAOI inhibitors) or which increase serotonergic tone (e.g. selective serotonin reuptake inhibitors (SSRIs), serotonin norepinephrine reuptake inhibitors (SNRIs), tricyclic antidepressants, triptans, amphetamines).
8. The patient has had a recent (within 6 months) cardiovascular event or clinically significant abnormal ECG finding at screening.
9. The patient has a history of Long QT Syndrome or a relative with this condition
10. The patient has expressed suicidal ideation within the past 3 months or is considered to be at risk of suicide.
11. The patient is morbidly obese (body mass index [BMI] ≥ 40 kg/m²) or has documented sleep apnea requiring CPAP or other treatment.
12. Female patient is pregnant and/or undergoing a pregnancy-related surgery, or breastfeeding.
13. The patient has a history of cardiopulmonary, neurological or psychiatric condition that may confound the assessments of efficacy or safety.
14. The patient has cirrhosis, moderate or severe hepatic impairment or an alanine aminotransferase (ALT) or aspartate aminotransferase (AST) value $> 3X$ upper limit of normal (ULN) at Screening.

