7.2.1. Post-Surgical Additional Exclusion Criteria

The patient is to be evaluated post-operatively prior to the initial treatment with the study drug and will be withdrawn prior to treatment with the study drug if any of the following exclusion criteria are met:

1. Patients who, in the opinion of the investigator, are not likely to tolerate the protocol's allowed analgesic regimen (tramadol plus non-opioid adjuvants).
2. Patients who have been admitted to the ICU post-surgery or have experienced complications during the surgical procedure that would put them at increased risk from receipt of the investigational product in the opinion of the investigator.
3. The patient is not clinically stable and not able to answer questions and follow commands.
4. The patient has evidence of respiratory insufficiency, such as a respiratory rate that is less than 8 breaths per minute or arterial oxygen saturation by pulse oximetry of less than 90% with supplemental oxygen.
5. Use of 5-HT₃ antagonists (e.g. ondansetron, granisetron, palonosetron) preoperatively, intraoperatively, or postoperatively

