14.3. Written Informed Consent

The Investigator(s) will ensure that the patient is given full and adequate oral and written information about the nature, purpose, possible risk and benefit of the study. Patients must also be notified that they are free to discontinue from the study at any time. The patient should be given the opportunity to ask questions and allowed time to consider the information provided.

The patient's signed and dated ICF and assent if applicable must be obtained before conducting any study procedures.

The Investigator(s) must maintain the original, signed ICF. A copy of the signed ICF must be given to the patient.

Protocol AVE-901-104 Phase 3 Open-Label Safety Study
Avenue Therapeutics, Inc.

Tramadol Infusion
August 29, 2018

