4.1. Analysis Populations

Three population are identified for purposes of the statistical analysis:

- Screened Population, defined as all screened patients.
- Screened Not Treated, defined as the subset of patients who are screened but not treated due to not moving forward to surgery or not meeting post-surgical dosing criteria.
- The Safety Population is defined as all patients who receive study medication. Patients will be analyzed according to the actual treatment they receive.

In general, data listings will include only subjects who receive study treatment (Safety population).

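### SAEs are collected only from the first dose, so a serious event arising from the protocol-required pre-surgical drug washout is not captured as an SAE

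*Protocol*

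**What the plan says.** **Start of collection.** Protocol 11.5: "Information about AEs and SAEs will be collected from treatment (i.e. from time of first dose) through the follow-up phone call". Anything earlier is reclassified: "AEs or SAEs occurring prior to first dose of study treatment will be considered Medical History". Protocol 11.2.1.2 repeats the window for serious events: "all SAEs that occur from treatment through the follow-up phone call should be recorded and reported as noted previously". Protocol 12.10.1 and SAP 9.2 carry the same Medical History rule into the analysis.

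**Washout as a condition of entry.** Under Protocol 7.2, exclusion 5 bars a patient on the listed CYP2D6/CYP3A4 inhibitors or CYP3A4 inducers who "cannot go through a minimum washout period of 7 days prior to surgery". Exclusion 7 reads "The patient cannot be withdrawn from medications (at least 7 days prior to surgery) that may lower the seizure threshold" and extends to drugs that raise serotonergic tone. Under Protocol 14.3, signed consent "must be obtained before conducting any study procedures".

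**Patients never dosed.** Protocol 7.2.1 sets further criteria after surgery; the patient "will be withdrawn prior to treatment with the study drug if any of the following exclusion criteria are met". SAP 4.1 names a Screened Not Treated group but says "In general, data listings will include only subjects who receive study treatment (Safety population".

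**The concern.** Starting the treatment-emergent definition at the first infusion is normal, and this point does not criticise it. The problem is that Protocol 11.5 applies the same start to collection and reporting. The statistical part of the synopsis is narrower: there, calling pre-dose events medical history is a convention for the analysis.

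The difference matters because the protocol makes something happen to some patients before the first dose. A patient taking one of the listed drugs has to come off it to qualify, and that falls in the interval in which no SAE is collected. If a serious event follows, the site has no SAE page to complete and the sponsor has no defined route by which to learn of it or to compare sites. Safety is the trial's primary objective, so serious harm from a step that the trial itself requires should reach the people overseeing it.

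**Working it through.** **1. The plan's own figure.** Protocol 12.1 and SAP 2.7 claim about 90% probability of at least one event at a true incidence of 1% with 250 patients. 1 − 0.99^250 = 1 − 0.081 = 0.919, so the claim reproduces. It depends only on the number treated and the incidence. Changing when SAEs are collected alters neither.

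**2. Where the washout falls.**
- Consent comes before study procedures (14.3), and screening runs from Day -28 to Day -1.
- The drug must be off for at least 7 days before surgery (7.2, exclusions 5 and 7).
- The first dose is given within 8 hours of meeting the post-surgical criteria (6.6.4), and SAE collection opens then (11.5).

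A washout made in order to enter the trial and begun after consent thus lies wholly before collection starts. This assumes screening at least 7 days before surgery. A patient screened later cannot fit the washout in after consent and must already be off the drug.

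**3. What a pre-dose event loses.** Protocol 11.4 requires onset, severity, causality, seriousness, action and outcome for each AE, and 11.5 requires SAE pages and prompt follow-up information. Neither document specifies any of these for medical history. The causality scale in 11.3 grades relation to the investigational product only, so it has no category for a washout event.

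**4. Where the event could still appear.**

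| Route | Patient later dosed | Patient never dosed |
|---|---|---|
| AE and SAE tables and listings | No, filed as medical history | No, Safety Population only |
| Medical history (Table 14.1.5, Listing 16.2.7) | Yes, without SAE fields | No, Safety Population only |
| Preoperative visit: history and eligibility (6.6.2) | Yes | Yes, if reached |
| Post-surgical evaluation and ECG before T0 (7.2.1, Table 4) | Yes | Yes, if reached |
| IRB notice of site SAEs (11.5) | Possibly; no start stated | Possibly; no start stated |
| Disposition (SAP 4.2, Table 14.1.1, all screened) | Not as a pre-dose event | Possibly, as a count under Adverse Event or Death |
| Follow-up call, Day 14 ± 2 from first dose (6.6.6) | Yes | No date to count from |

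I could not read where the adverse-event row of Table 4 begins, so I rely on 11.5, which is explicit.

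**5. Size.** The documents give neither the number washed out nor a risk of serious events during washout. As an illustration only, assume 5% to 30% of 250 patients are washed out (12 to 75) and that the risk is 0.5% to 2%. The chance of at least one such event is then:
- lowest: 1 − 0.995^12 = 0.058
- middle: 1 − 0.99^25 = 0.222 (10% washed out, 1% risk)
- highest: 1 − 0.98^75 = 0.780

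A range of 6% to 78% reflects the assumptions and is not an estimate.

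**The case against.** The case for leaving the plan alone is a serious one.

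- **Consistency.** Protocol and SAP agree, and the stated objective is the safety of IV tramadol, not of preoperative drug withdrawal. This stands: it is a design choice, and no requirement in the documents is breached.
- **Other checks exist.** A reader might infer that the trial could not detect or act on serious harm during washout, or that nothing is scheduled between the preoperative visit and the first dose. The documents support neither. The preoperative visit, within 24 hours of surgery, repeats history and eligibility, including the suicide-risk exclusion, and can stop entry. After surgery there is a further evaluation and an ECG before dosing. Investigators are asked to notify the IRB of all SAEs at their site, and disposition covers all screened patients. For dosed patients the event should be visible in the medical-history outputs.
- **Entry criteria reduce the risk.** Exclusions 1, 10 and 13 and the limit to ASA class 1 or 2 remove many of the patients most vulnerable to withdrawal. They do not remove all, since exclusion 7 still allows patients on antipsychotics or antidepressants to enter after stopping them.

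These checks do not replace SAE capture. Site-level IRB notice gives the sponsor no view across sites, and the Medical History rule in the same section leaves it arguable whether that notice reaches pre-dose events. A disposition count carries no narrative or causality, and the completion listing (16.2.5) covers only the Safety Population.

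**Conclusion.** The point holds in a limited form. A serious event arising from the washout required by exclusions 5 and 7 is not captured as an SAE. It gets no SAE page, seriousness or causality assessment, or defined sponsor report. For a consented patient who is never dosed, it appears in no AE, SAE or medical-history output. It may still surface by the other routes, so such an event would not necessarily go unseen.

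No magnitude can be given. It is tempting to assume a washed-out fraction and quote a number of patients affected, but nothing in the documents supports any particular fraction. Nor should every consented but undosed patient be counted, since the washout applies only to those taking the listed drugs.

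The conclusion rests on two readings: that 11.5 means what it says about collection, and that a washout made to qualify for the trial follows consent. It is an inexpensive improvement to patient safety and sponsor oversight, not a flaw in the planned analysis.

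**What to change.** - Amend Protocol 11.5 and 11.2.1.2 so that, from informed consent, at least those SAEs that the investigator links to a protocol-required procedure, including medication washout, are collected and reported.
- Add an eCRF flag recording that link, because the scale in 11.3 covers only the investigational product.
- For consented patients never dosed, record these SAEs until withdrawal, and follow any still open to resolution under the follow-up provision already in 11.2.1.2.
- Add one pre-treatment SAE listing to the SAP, on the Screened Population. Leave the treatment-emergent definition and tables, and the Safety Population, unchanged.

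The cost is amendment wording, the flag, one listing and a few additional SAE forms. The sample size of 250 and the probability of about 92% are unaffected. The change takes no position on whether or how any drug should be withdrawn.
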